The Psychology Department has its own clinic with a full-time clinic director and administrative assistant. The physical space includes four individual treatment rooms, 1 group therapy room, and four individual assessment rooms. The clinic is available for project-related referrals. The Department of Psychology also makes available significant computer resources to grant funded projects, including workstations, servers, secure networks, and technical personnel. The Department's connection to the Internet is via multiple redundant Gigbit optical fiber links, and all network traffic passes through a protective firewall. All out-world access to Fileservers holding research data require secure encrypted VPN connections, and all workstations and servers require passwords for access. The Department has well over 800 computer workstations, and about 24 web/file/streaming-video servers hosting nearly 10 Terabytes of data. The Departmental technical support staff consists of 7 full-time technicians including web, audio-video, database, security, and computer publications specialists.

Institute for Mental Health Research (IMHR)

The IMHR is an organized research unit with the College of Liberal Arts that reports to the Dean of the College of Liberal Arts. All faculty have appointments in academic departments but research effort occurs within the IMHR. In January 2015, the IMHR moved into research space located in College of Liberal Arts (CLA) Building. This space was selected because it is centrally located on campus, accessible and identifiable to research participants who are unfamiliar with campus, and there is substantial room for expansion. The IMHR initially includes approximately 8,000 square feet of dedicated office and research space that will contain research labs tailored to the needs of each investigator, a participant waiting room, a conference room, three therapy/assessment rooms, a computer lab for data processing and analysis, a biospecimen collection and storage room (with centrifuge and freezers), office space for faculty, staff, post-doctoral fellows, and graduate students, a break room, and a mailroom.

CLA is very close to the heart of campus (where many undergraduate classes are held) and a 10-minute walk to the Department of Psychology. This space will allow IMHR faculty members to work in state-of-the-art facilities designed to foster collaboration and innovation while simultaneously allowing IMHR faculty to access collaborators and resources from around the campus community.

Anxiety & Health Behaviors Laboratory

The Anxiety & Health Behaviors Laboratory is located within the Institute for Mental Health Research (see below) and is also affiliated with the Department of Psychology at the University of Texas at Austin. The laboratory is directed by [name], professor and licensed psychologist. Other personnel include [name], licensed psychologist and [name], a board-certified psychiatrist. The laboratory is further staffed by two research staff members, and 5 doctoral students, who are trained and certified in the conduct of diagnostic evaluations as well as the delivery of behavioral interventions for anxiety and smoking cessation.

The Anxiety & Health Behaviors Laboratory consists of two adjacent research suites and a research office. The testing suite contains three individual testing rooms and an office for the laboratory manager. This testing suite, which will be used for ABR and CTRL training, is sound attenuated with multiple layers of soundproof gypsum board specifically designed for this purpose, and houses the human psychophysiology of emotion equipment (see below). The exercise suite consists of a room that houses the exercise equipment (see below) and a locker room with shower. The research office contains filing cabinets and equipment (e.g., two iMac

desktop computers, phones, etc.) required for staff to support research efforts (e.g., screening, scheduling, data entry/analysis). All rooms are networked and equipped with state-of-the-art computers. All staff, including [name], has offices located nearby in the IMHR, allowing for close contact between research staff and key personnel on this project.

Human Psychophysiology of Emotion Equipment

[name] is equipped with a psychophysiological suite that allows assessment of psychophysiological responses associated with symptoms of mood, anxiety, and substance use disorders using state-of-the-art technology. The lab has an acoustic startle system coupled to the BIOPAC MP150 Psychophysiological Recording Apparatus that allows us to measure acoustic startle (electromyogram, EMG), and skin conductance (GSR). The Human Psychophysiology of Emotion set up contains three iMac desktop computers and Dell PC all for the purposes of stimulus presentation (SuperLab 4.0, Cedrus Corporation, San Pedro, CA), data collection (AcqKnowledge 4.0), and psychophysiological data analysis (Mindware, Mindware Technologies, Gahanna, OH).

Exercise Equipment

[name] is equipped with a Cybex 770 AT total body arc trainer and The Cybex 770T treadmill. The exercise machines face two individual TV screens and are connected to polar heart rate monitors. The exercise suite also is equipped with an AED and telephone.

RedCap

Study data will be collected and managed using REDCap (Research Electronic Data Capture). REDCap is a secure, web application designed to support data capture for research studies, providing user-friendly web-based case report forms, real-time data entry validation (e.g. for data types and range checks), audit trails and a de-identified data export mechanism to common statistical packages (SPSS, SAS, Stata, R/S-Plus). REDCap also provides a powerful tool for building and managing online surveys. The research team can create and design surveys in a web browser and engage potential respondents using a variety of notification methods. The system was developed by a multi-institutional consortium that includes University of Texas at Austin and was initiated at Vanderbilt University. The database is hosted at the University of Texas. The REDcap server has been cleared for Category-I data by UT's Information Security Office. Network transmissions (data entry, survey submission, web browsing, etc.) in REDCap are protected via Secure Sockets Layer (SSL) encryption. REDCap data collection projects rely on a thorough study-specific data dictionary defined in an iterative self-documenting process by all members of the research team with planning assistance from the PRC. The iterative development and testing process results in a well-planned data collection strategy for individual studies. REDCap provides a secure, web-based application that is flexible enough to be used for a variety of types of research, provide an intuitive interface for users to enter data and have real time validation rules at the time of entry. The REDCap Consortium is composed of 681 active institutional partners in 58 countries. The consortium supports a secure web application (REDCap) designed exclusively to support data capture for research studies.

DATA SHARING PLAN

We will provide de-identified data from this project to interested individuals one year following achievement of the aims of the project (i.e., publication of main outcome paper). These data will be provided in digital format (i.e., disk), with clear labels for all variables. Data will be released directly by [name] team to investigators providing evidence of their institution's IRB approval for planned analyses of the data. [name] team will be available to address queries.

BIBLIOGRAPHY

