We have a history of successful recruitment for NIH-funded trials of smoking cessation interventions and will use the approach that has been effective in these studies. Specifically, we will advertise through numerous community organizations that promote quit smoking initiatives and also use social media and Internet outlets to advertise our study. The greater Austin, TX area has a population of 1.9 million. The enrollment period will be 127 weeks (of 156 weeks), allowing sufficient time for start-up activities (12 weeks) and participants to complete the study protocol (17 weeks) and complete data analysis (starting at week 139). Accordingly, we need to enroll 0.8 patients every week or 4 patients every 5 weeks. Currently, we screen, on average, 22.45 individuals weekly (or 112 every five weeks) for ongoing smoking cessation studies. Given the required conversion rate is 4% (4 of 112), we deem this targeted enrollment feasible.

C3c. Screening Procedures

An initial web screen will be performed with all potential participants to determine initial eligibility (e.g., smoking history, motivation to quit). A UT staff member will contact potential participants who appear eligible following screen to provide more details about the study and, if the participant provides informed consent, the staff member will conduct the Mini International Neuropsychiatric Interview (MINI)^{41,42} to assess psychiatric exclusion criteria. Participants who are eligible and remain interested will be enrolled.

C4. Procedures

C4a. Randomization and Baseline Visit

Eligible participants will be randomized to study condition prior to the baseline visit. The project biostatistician, [name], will oversee the randomization. He will use variable-sized permuted block-randomization (block sizes will vary from 4 to 12). Prior to data analyses, [name] will check the balance of randomization and control for any factors that are imbalanced. The baseline visit serves to obtain initial assessments on the outcome and mechanisms variables.

C4b. Interventions

Participants will receive a standard, individual smoking cessation treatment based on the most recent clinical practice guideline from the U.S. Department of Health and Human Services, Treating Tobacco Use and Dependence³. Consistent with the manualized procedures we have employed in past and ongoing NIDA-funded investigations⁴³⁻⁴⁶, the standard intervention (ST) involves a combination of CBT plus NRT.

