As in past an ongoing work⁴³⁻⁴⁶, self-reported smoking status will be assessed during the intervention (weeks 0-7), at posttreatment (week 8), and at 1-month (week 9), 2-month (week 13) and 3-month (week 17) follow-up (i.e., post-quit; see Figure 6). Self-reported abstinence will be verified by expired carbon monoxide (CO). Abstinence at the 2-month (week 13) and 3-month (week 17) follow-up will additionally be verified with saliva cotinine. We will use the timeline follow-back (TLFB) procedure at all assessments to assess cigarette consumption at each day following the previous assessment, which has demonstrated good reliability and validity⁴⁹. Self-reported abstinence will be overridden by a positive carbon monoxide ($\geq 4\text{ppm}$)⁵⁰ or saliva cotinine verification ($>10 \text{ ng/mL}$)⁵¹. If neither CO nor cotinine levels are available to verify abstinence at an assessment, abstinence will be considered missing data⁵². We will employ 7-day point prevalence abstinence (PPA) and prolonged abstinence (PA) as the primary outcomes. PPA will be defined as no smoking, not even a puff, in the 7 days prior to any assessment. Failure to maintain PA at any assessment will be defined by smoking on 7 consecutive days or smoking at least once each week over 2 consecutive weeks⁴⁰.

Figure 6. Assessment Schedule

| | Protocol Weeks | | | | | | |
|--|----------------|----------|----------|-----------|------------------|---------------|-------------------------------|
| | -3,-2,-1 | 0 | 1-4 | 5 | 6 | 8 | 9-17 |
| | End Points | | | | | | |
| | Pre-Screen | Baseline | Pre-Quit | Quit Week | 1-Week Follow-up | Posttreatment | 1-, 2-, and 3-Month Follow-up |
| Screening | | | | | | | |
| Demographics | X | | | | | | |
| Smoking history | X | | | | | | |
| Motivation to quit | X | | | | | | |
| Nicotine dependence (FTND) | X | | | | | | |
| Psychiatric diagnosis and suicide (MINI) | X | | | | | | |
| AIM 1: Efficacy | | | | | | | |
| Self-reported smoking (TLFB) | | X | X | X | X | X | X |
| Carbon monoxide | | X | X | X | X | X | X |
| Saliva cotinine | | | | | | | X ¹ |
| AIM 2: Mechanisms of Action | | | | | | | |
| Craving (QSU-B) | | X | X | X | X | | |
| Approach Bias (AAT; session data) | | X | X | X | | | |

¹ Only assessed at 2- and 3-month follow-up

C5c. Mechanisms of Action

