We will use the Questionnaire of Smoking Urges-Brief (QSU-B⁵³), which is a psychometrically sound measure of craving. We will administer the AAT^{14,18,22} in order to assess approach bias at baseline. The ATT instructs participants to pull a joystick upon seeing an image tilted to the right and to push the joystick upon seeing a left-tilt image, while ignoring the image content (i.e., indirect instructions). By pulling the joystick (approach), the picture grows in size; by pushing the joystick away (avoidance), the picture shrinks. The AAT includes 96 trials in which each of 24 smoking-related pictures (e.g., woman lighting a cigarette) and each of 24 positive images (e.g., group of friends exercising) will be pulled and pushed. An approach bias score for smoking-related pictures will be computed for each participant by subtracting the average time it takes to pull smoking-related images from the average time it takes to push away these images. Thus, a positive value indicates an approach tendency toward smoking stimuli, whereas a negative value is indicative of avoidance of smoking images. As discussed in section C4a, the ABR also involves 12 incompatible smoking-related trials in the last half of each training session, allowing us to compute the approach bias at the end of each of the seven training sessions in ABR^{11,14}. Specifically, the approach bias score will be computed by subtracting the average time it takes to pull smoking-related images (the 12 incompatible trials in the second half of each session) from the average time it takes to push smoking-related images (48 trials). Similarly, we will compute an approach bias score for the end of each of seven CTRL training sessions by subtracting the average time it takes to pull smoking-related images (the 24 incompatible trials in the second half of each session) from the average time it takes to push smoking-related images (the 24 compatible trials in the second half of each session)^{11,14}. Finally, we will explore scoring algorithms for the AAT and session data that standardize the bias scores by dividing an individual's difference in response times by a personalized standard deviation of these response latencies. A similar scoring approach has been used successfully for a related task, the Implicit Association Test (IAT⁵⁴).

C6. Training and Quality Assurance/Quality Control

C6a. Checks of Integrity of Screening Procedures

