We will use the same procedures as in ongoing and previous studies^{43–46}. Personnel involved in screening will be certified in diagnostic interviewing. Certification will involve attending a workshop provided by [name] and successful screening of 5 potential participants under supervision of certified personnel.

C6b. Checks of Integrity of Treatment Procedures

Drs. [name] will provide in-person training and supervision to [name], who will deliver the CBT sessions. Adherence scores will be used as part of supervision, which will occur on a monthly basis.

Approach bias retraining latencies will be checked for treatment integrity. Training trials with errors (i.e., participants pushed when they should have pulled and vice versa) and unusual response latencies (i.e., very long (> 2000ms) or very fast (< 200ms) trials) will be dropped. Training integrity for a given session will be considered unacceptable when 20% or more of the trials are dropped. Based on our past experience, we expect high levels of training integrity^{10–12,14}.

C7. Participant Adherence and Incentives for Participation

We will utilize a number of strategies in efforts to promote adherence and retention. Prior to randomization, participants will have completed an extensive screening process. Participants will also be provided a behavioral expectations document informing them of the requirements of their assigned group.

[name], supervised by Drs. [name], will manage retention of the participants. She will be able to meet with participants on 6–7 days of the week for their sessions. If a participant misses a session, she will call to check in, encourage attendance, and help problem solve if a barrier to participation is present. [name] will also monitor adherence to the assessment schedule. She will place reminder calls/emails to participants three days prior to each scheduled follow-up session. Participant self-reported abstinence will be verified for each of these major end point assessments.

Finally, we will provide \$250 per individual (i.e., \$50 for completing each major outcome assessment; weeks 0, 6, 9, 13, and 17) as an incentive for participation in the study. We think this amount is appropriate given the amount of time required for completing the assessments.

C8. Data Analysis

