As per our pre-registered analysis plan ([name] et al., 2019), we examined the equivalence of the treatment groups on demographic and key psychological variables prior to treatment; variables on which the groups differed were included as covariates in the final analyses if they were significantly related to outcome. The only variable that differed between groups was the initial avoidance tendency score ($t(94) = 2.88$, $p = 0.005$), which was added as a covariate in all analyses. A priori power analysis indicated greater than 0.80 power to detect a significant condition effect if the abstinence rate in ST+ABR was 42 % or greater (effect size $\omega = .238$) with a sample size of 100 (see [name] et al., 2019 for more details).

PROTECTION OF HUMAN SUBJECTS

Risks to Subjects

Human Subjects Involvement and Characteristics

We plan to enroll 100 participants total. The participant population will be comprised of both males and females of mixed ethnic and socioeconomic backgrounds. All participants meeting entrance criteria will be offered the opportunity to participate. Participants will not be excluded on the basis of gender or race. Inclusion and exclusion criteria are presented in the Figure 7.

Figure 7. Study Entry Criteria

| Inclusion Criteria | |
|-------------------------------|---|
| 18 to 65 years old | |
| Informed consent | The capability and willingness to give written informed consent, to understand inclusion and exclusion criteria, and to accept the randomized group assignment are required. |
| Daily smoker | Smoking status will be assessed via self-report at screening. Only participants who currently smoke ≥ 10 cigarettes per day can be eligible. |
| Motivated to quit | Reporting motivation to quit smoking (>5 on a 0-10 scale). |
| Exclusion Criteria | |
| Use of other tobacco products | Use of tobacco products, including e-cigarettes, will be assessed during screening. |
| Psychiatric disorders | Currently suicidal or high suicide risk, current or past psychotic disorders of any type, bipolar disorder (I, II, or NOS), schizophrenia or schizoaffective disorder, anorexia, bulimia, alcohol or substance dependence within the last 6 months, patients with comorbid psychiatric conditions that are relative or absolute contraindications to the use of any treatment option in the protocol. These will be assessed by the MINI. |

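### Randomisation precedes the baseline visit, so the initial avoidance score adjusted for in every analysis is a post-randomisation measure of unstated source

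*Combined protocol and SAP*

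**What the plan says.** Section C4a sets the order: "Eligible participants will be randomized to study condition prior to the baseline visit". It then gives the purpose of that visit: "The baseline visit serves to obtain initial assessments on the outcome and mechanisms variables".

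The assessment schedule (Figure 6) agrees. TLFB, CO, QSU-B and AAT have their first mark in the week-0 column and none at pre-screen. The approach-bias row, for example, reads "Approach Bias (AAT; session data) | | X | X | X", with the empty first cell being pre-screen. C5c says the AAT is given "in order to assess approach bias at baseline". Demographics, smoking history, motivation, nicotine dependence and the psychiatric interview are pre-screen items, so they precede assignment and are not in question here.

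Two kinds of arm-related material are described. C7 says "Participants will also be provided a behavioral expectations document informing them of the requirements of their assigned group" and gives no date for it. C4b gives the two arms different explanations of what their computer training does, also without a stated moment of delivery.

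C8 reports a balance check on variables described as prior to treatment. One variable differed, the initial avoidance tendency score (t(94) = 2.88, p = 0.005), "which was added as a covariate in all analyses". C8 also uses the initial score as an exploratory moderator.

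**The concern.** A covariate is safe to adjust for when assignment cannot have affected it. Measuring it before assignment guarantees that. Measuring it afterwards makes the guarantee depend on what participants and staff knew, and on whether training had begun. The documents settle neither.

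The source of the score is also open. C5c defines an approach-bias score, not an avoidance tendency score. C8 models avoidance scores over the seven weeks of training, so the initial value could be the week-0 AAT or the score from session 1. The two cases differ:

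- **Week-0 AAT:** post-randomisation but before training. It works as a proper baseline if the arm was not known at the time.
- **Session-1 score:** post-randomisation and during training. An arm difference may then be an early effect of the training, and adjusting for it could remove part of the effect the trial sets out to estimate.

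The trial exists to supply effect-size data for a larger study. The abstinence estimate is adjusted for the one checked variable that differed by arm, and the reader cannot tell which case applies.

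**Working it through.** **1. The reported test.** Input from C8: t = 2.88 on 94 degrees of freedom. The two-sided p value is 2 × P(T94 > 2.88) = 0.0049, which matches the stated 0.005.

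**2. Size of the difference.** 94 degrees of freedom imply 94 + 2 = 96 people with a score. Arm sizes are not given, so 48 and 48 is assumed.

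d = t × √(1/n1 + 1/n2) = 2.88 × √(2/48) = 0.588 SD, approximate 95% CI 0.18 to 1.00.

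A 40/56 split gives 0.596, so the assumption hardly matters.

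**3. Could it be chance?** The number of variables checked, k, is not stated. If allocation affected none of them and they were independent, the chance of at least one p value this small is 1 − (1 − 0.0049)^k:

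| k (assumed) | Probability |
|---|---|
| 1 | 0.5% |
| 5 | 2.4% |
| 10 | 4.8% |
| 20 | 9.4% |

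The imbalance is unusual, but chance is not excluded.

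**4. How far adjustment moves the estimate.** To a first approximation, shift in log odds ratio = b × d, where b is the score's log-odds coefficient per SD. The documents give no b, so a range is assumed. For scale, C8 gives 42% abstinence in ST+ABR and an effect size of .238. A control rate of 20% reproduces that effect size: (0.42 − 0.20) / (2 × √(0.31 × 0.69)) = 0.238. The planned log odds ratio is then ln[(0.42/0.58) / (0.20/0.80)] = 1.06.

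| b per SD (assumed) | Shift = 0.588 × b | Share of 1.06 |
|---|---|---|
| 0.2 | 0.12 | 11% |
| 0.3 | 0.18 | 17% |
| 0.5 | 0.29 | 28% |

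The same shift occurs if the imbalance is pure chance, and it is then a correction. It is bias only to the extent that assignment caused the difference. If the caused part lies between none and all of the observed 0.588 SD, each figure is a ceiling for its b. The documents do not say which arm scored higher, so the direction cannot be read from them, though the trial data would show it.

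**5. What a session-1 score would contain.** C4b gives ABR participants 96 smoking images to push per session, and C5c takes 48 of those pushes from the scored part. The 12 pull trials used for scoring fall in the second half. An ABR participant has therefore pushed about 96 − 48 = 48 smoking images before the scored trials begin. A control participant has 48 pushes and 48 pulls of smoking images per session, with 24 of each scored in the second half, leaving 24 of each in the first. On this reading the arms have had different exposure before the score is taken.

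**The case against.** The strongest reply is that order alone biases nothing; assignment must be known, or treatment begun. The trial is called double-blind (A5 and the C2 study overview). The schedule puts the AAT at week 0 and the pre-quit sessions in weeks 1 to 4. The arm rationales are described as part of the training, and C8 calls the checked variables prior to treatment. The AAT is an indirect reaction-time task, the two rationales are meant to create similar expectations, and the expectations document need not reveal the arm because both groups attend the same visits. All of this stands, and it makes a harmless sequence plausible. It does not establish one: the documents do not say who knew the allocation at week 0, when the arm-related material was given, or which measurement supplied the score.

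A reader might infer three stronger conclusions, none of which the documents support.

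- **That the 11% to 28% is the bias.** It is the movement produced by adjusting, under assumed coefficients, and is bias only if assignment caused the entire difference.
- **That the unadjusted estimate should become the main one.** C4a and C8 state in advance that imbalanced factors will be controlled. Reversing that once results are known is a trade-off, and if the imbalance is chance it leaves about 0.59 SD uncorrected.
- **That participants were lost between assignment and week 0.** 96 scores against a planned 100 could equally reflect under-enrolment or unusable task data. No such loss is reported.

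**Conclusion.** The sequence is explicit, and the covariate is post-randomisation on either reading of its source. It differed by about 0.59 SD between arms and enters every analysis. Whether that does harm is undetermined. If the score is the week-0 AAT and allocation was concealed then, the adjustment is valid. If it is the session-1 score, it was taken during training and adjusting for it could absorb part of the treatment effect.

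The ceiling on bias in the treatment log odds ratio is 0.12 to 0.29. This rests on near-equal arms, coefficients of 0.2 to 0.5 per SD, and assignment having caused the whole difference. The weakness is cheap to remove and merits a change in design and reporting. It is not grounds for discarding the adjusted result.

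**What to change.** 1. **Sequence (C4a).** Release the allocation at the end of the week-0 visit, after AAT, QSU-B, CO and TLFB are recorded and before any arm-specific document or rationale is given. The block list need not change. Because C8 already reports results, this mainly serves the planned follow-up trial.
2. **Covariate (C5c and C8).** Define the avoidance tendency score, and specify that any bias covariate is the week-0 AAT and not a training-session score.
3. **Data already collected.** Keep the pre-specified adjusted model and report the abstinence effect without this covariate beside it. State which measurement supplied the score and who knew the allocation when it was taken. Some difference between two logistic estimates is expected merely from conditioning on a predictor, so a gap is not in itself evidence of bias.

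The cost is one sentence in C4a, a later moment for opening the allocation, a definition, and one extra model. No new visits, staff or participants are needed.
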